2.2.2.3 Toxicology

Consistent with the International Council for Harmonisation (ICH) S6 (R1) guidance (ICH, 2011), the studies conducted in the nonclinical safety assessment of AMG 133 included in vitro genotoxicity studies, a tissue cross-reactivity study, and exploratory 4-week subcutaneous (SC) repeat-dose and pivotal Good Laboratory Practices-compliant 13-week SC repeat-dose toxicology studies conducted in the mouse and the cynomolgus monkey. The GLP-1 analog peptide portions of AMG 133 contain a non-natural amino acid; the GLP-1 analog peptide was tested for genotoxicity in the bacterial reverse mutation and in vitro human peripheral blood lymphocyte micronucleus tests and did not show any evidence of genotoxic activity in either test. The anti-GIPR mAb in AMG 133 has very high amino acid identity with AMG 598, Amgen's anti-GIPR mAb (IND 135844). Therefore, the results of the tissue cross-reactivity study in a full panel of human tissues with biotin-labeled AMG 598 is considered applicable to AMG 133; no potential AMG 598 cross reactivity in human tissues was identified.

AMG 133 was administered to mice in a 4-week exploratory toxicology study and a 13-week repeat-dose toxicology study. Despite the lower potency of AMG 133 for mouse GIPR, the high exposures obtained in the repeat-dose toxicology studies in the mouse likely achieved at least partial GIPR antagonism. In the 4-week exploratory toxicology study in the mouse, administration of AMG 133 by SC injection once weekly for a total of 4 doses was well tolerated up to 141 mg/kg. The highest tested dose of 658 mg/kg was not tolerated due to severe clinical signs of dehydration. In the pivotal 13-week repeat-dose toxicology study in mice, administration of 25, 75, and 150 mg/kg AMG 133 by SC injection once every 2 weeks for a total of 7 doses was well tolerated, with dose-dependent mild transient clinical observations of suspected dehydration.

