In the 4-week exploratory toxicology study in the monkey, weekly SC administration of 11, 56, and 188 mg/kg AMG 133 was well tolerated, and dose-dependent body weight loss was observed. In the pivotal 13-week toxicology study, once every 2 weeks SC administration of 20, 60, or 120 mg/kg AMG 133 for 13-weeks (7 total doses) induced dose-independent body weight loss, indicating maximum pharmacological activity at all tested doses. In the pivotal 13-week study, there were no AMG 133-related effects on clinical observations, neurologic or ophthalmic examinations, quantitative and qualitative electrocardiography, vital signs, fasting blood glucose or insulin, coagulation and urinalysis parameters, biochemical biomarkers for bone metabolism, or organ weights. Nonadverse minimal to mild decreases in red blood cell parameters (hemoglobin, hematocrit, red blood cell counts) and reticulocyte counts were present in both studies in the monkey. 1 female at 120 mg/kg in the 13-week study also had changes in red blood cell morphology and a minimal increase in total bilirubin, suggestive of an increased red blood cell turnover; this change was considered nonadverse due to the small magnitude and lack of clinical observations or evidence of microscopic changes in the liver or gall bladder. There were no macroscopic or microscopic changes in the monkey directly related to AMG 133, including in the pancreas; light microscopic observations of minimal to mild SC mononuclear cell infiltrates at the injection site were considered an anticipated localized response to the SC administration of an exogenous protein. In the pivotal 13-week toxicology in the cynomolgus monkey, the NOAEL was the highest tested dose of 120 mg/kg.

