4.3 Justification for Investigational Product Dose

The planned cohort in this amendment of the study consists of a multiple-dose cohort following a titration schema as presented in [Figure 1-1](#).

Previously, subjects in Part A received single doses of AMG 133 - 21, 70, 140, 280, 560, and 840 mg administered SC. This part also consisted of an IV cohort (cohort 6) at a dose of 70 mg administered IV; **all SAD** have been completed. The starting dose and exposure multiples for the doses evaluated in SAD were calculated based on the NOAELs determined in the 13-week Good Laboratory Practices repeat-dose mouse and cynomolgus monkey nonhuman primate toxicology studies (every 2 weeks dosing, Section 2.2.2.3) and the observed reduction in body weight in the chronic efficacy study in obese cynomolgus monkeys.

Part B consisted of evaluation of AMG 133 **following repeat doses - 140, 280, and 420 mg administered Q4W for a total of 3 doses per cohort.** Preliminary review of the PK data in the FIH SAD **and MAD** part of the study demonstrated that AMG 133 pharmacokinetics follow a linear, dose proportional kinetics based on C_{max} (area under the curve [AUC] data pending), with a half-life of approximately **15 to 20 days**.

For **SAD cohorts 1 to 6 and 11**, no **serious adverse events** or deaths have been reported, and most **adverse events** reported were mild associated with nausea, vomiting, **and dyspepsia**. One subject in cohort 3 (140 mg dose) had a moderate adverse event associated with gastroenteritis **related to IP**. **Approximately 90% of subjects enrolled in MAD cohorts 7 to 10 reported mild GI-related adverse events (mainly nausea, vomiting, and diarrhea) after the first dose of AMG 133 and less than 5% experienced GI-related adverse events after the second dose.** There were **no serious adverse events or deaths reported after any of the doses**.

Approximately 26% of subjects in the MAD trial discontinued the study prior to

receiving the second dose which caused concerns regarding tolerability of the first dose; 50% of subjects in cohort 9 withdrew consent after receiving the 420 mg dose on day 1 due to GI-related adverse events. The doses were selected to allow for whole integer injection volumes to circumvent any potential dosing errors.

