Part C consists of two cohorts (cohorts 12 and 13), both open-label to evaluate dose-level escalation from 70 mg to 420 mg. The objective of Part C is to evaluate first dose effects of AMG 133 on GI-related adverse events using a titration methodology. Cohort 12 will start at a lower dose [redacted] mg) of AMG 133 given [redacted]

Cohort 13 will start at a lower dose ([redacted] mg) of AMG 133 given [redacted]

The rationale for dose selection for Part C is based on the available PK data from this ongoing FIH study cohorts 1 to 11 (Part A and Part B) and the NOAEL exposures established based on 13-week GLP repeat-dose studies in mouse and cynomolgus monkeys.

Similarly, for cohort 12, the predicted human exposure multiples for intact AMG 133 following the second dose of [redacted] mg on Day [redacted] are approximately 40.5-fold and 45-fold for C_{max} and AUC_{ss} , respectively, based on NOAEL established in cynomolgus monkeys, and 43-fold and 42.4-fold for C_{max} and AUC_{ss} , respectively, based on NOAEL established in mice. The predicted human exposure multiples for total AMG 133 following the second dose of [redacted] mg on Day [redacted] are approximately 45-fold and 49-fold for C_{max} and AUC_{ss} , respectively, based on NOAEL established in cynomolgus monkeys, and 54-fold and 42-fold for C_{max} and AUC_{ss} , respectively, based on NOAEL established in mice (Table 8 and Table 9).

For cohort 13, the predicted human exposure multiples for intact AMG 133 following the second dose of [redacted] mg on Day [redacted] are approximately 39-fold and 43.2-fold for C_{max} and AUC_{ss} , respectively, based on NOAEL established in cynomolgus monkeys, and 41.3-fold and 40.6-fold for C_{max} and AUC_{ss} , respectively, based on NOAEL established in mice. The predicted human exposure multiples for total AMG 133 following the second dose of [redacted] mg on

Day █ are approximately 42.2-fold and 45.5-fold for C_{max} and AUC_{ss} , respectively, based on NOAEL established in cynomolgus monkeys, and 50.9-fold and 47.5-fold for C_{max} and AUC_{ss} , respectively, based on NOAEL established in mice (Table 8 and Table 9).

Table 8. Estimated Exposure Margins of Intact AMG 133 Following Repeat Doses (Q4W)

Clinical Dose (mg)	Route	Predicted Human Exposure		Predicted Exposure Multiples ^a			
		AUC ₀₋₂₈ (μ g·hr/mL)	C_{max} (μ g/mL)	Mouse ^b		Monkey ^c	
█ (cohort 12) ^f	SC	17 731	37	42.4	43	45.1	40.5
█ (cohort 13) ^f	SC	18 513.6	38.5	40.6	41.3	43.2	39

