AUC = area under the concentration-time curve; AUC_{last} = area under the concentration-time curve during a last dosing interval; AUC_{0-28} = area under the concentration-time curve during a dosing interval defined here from time 0 to 28 days after the 2nd dose; C_{max} = maximum observed drug concentration during a dosing interval defined here after the 2nd dose; FIH = First in Human; NOAEL = no observed adverse effect level; PK = pharmacokinetic; SC = subcutaneous; Q4W = every 4 weeks.

^a PK data from AMG 133 FIH study is used for PK prediction

^b After the last dose after 13 weeks of treatment (7 total doses) at the NOAEL dose of 150 mg/kg in mice (Study 150238); mean AUC_{last} ($AUC_{0-168hrs}$) of 188 000 μ g·hr/mL and mean C_{max} of 1590 mg/mL of Intact AMG 133.

^c After the last dose after 13 weeks of treatment (7 total doses) at the NOAEL dose of 120 mg/kg in cynomolgus monkeys (Study 150239); mean AUC_{last} ($AUC_{0-168hrs}$) was 200 000 μ g·hr/mL and mean C_{max} of 1500 mg/mL of Intact AMG 133.

^d AUC exposure multiples = ratio of AUC_{last} after 13 weeks (7 doses) of AMG 133 administration in the mouse or monkey x 4/predicted AUC_{0-28} in humans after the 2nd dose.

^e C_{max} multiple = the ratio of C_{max} after the last dose after 13 weeks (7 doses) of AMG 133 in the mouse or monkey to the predicted C_{max} for each human single dose.

^f Actual dose levels will be based on available data from previous cohorts.

Source: Report 153788

Table 9. Estimated Exposure Margins of Total AMG 133 Following Repeat Doses (Q4W)

Clinical Dose (mg)	Route	Predicted Human Exposure		Predicted Exposure Multiples ^a			
		AUC _{tau} (μ g·hr/mL)	C_{max} (μ g/mL)	Mouse ^b		Monkey ^c	
█ (cohort 12) ^f	SC	22 831	43.5	51	54.3	48.9	45.1
█ (cohort 13) ^f	SC	24 504	46.4	47.5	50.9	45.5	42.2

AUC = area under the concentration-time curve; AUC_{0-28} = area under the concentration-time curve during a dosing interval defined here from time 0 to 28 days after the 2nd dose; C_{max} = maximum observed drug concentration during a dosing interval defined here after the 2nd dose; FIH = First in Human; NOAEL = no observed adverse effect level; PK = pharmacokinetic; SC = subcutaneous; Q4W = every 4 weeks.

^a PK data from AMG 133 FIH study is used for PK prediction

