^b After the last dose after 13 weeks of treatment (7 total doses) at the NOAEL dose of 150 mg/kg in mice (Study 150238); mean AUC_{last} (**AUC_{0-168hrs}**) of 291 000 µg hr/mL and mean C_{max} of 2360 mg/mL of Total AMG 133.

^c After the last dose after 13 weeks of treatment (7 total doses) at the NOAEL dose of 120 mg/kg in cynomolgus monkeys (Study 150239); mean AUC_{last} (**AUC_{0-168hrs}**) was 279 000 µg hr/mL and mean C_{max} of 1960 mg/mL of Total AMG 133.

^d AUC exposure multiples = ratio of AUC_{last} after 13 weeks (7 doses) of AMG 133 administration in the mouse or monkey x 4/predicted (**AUC_{0-28 days}**) in humans after the **2nd** dose.

^e C_{max} multiple = the ratio of C_{max} after the last dose after 13 weeks (7 doses) of AMG 133 in the mouse or monkey to the predicted C_{max} for each human single dose.

^f Actual dose levels will be based on available data from previous cohorts.

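### The Part C AUC safety margins scale a one-week animal AUC by 4 although the animals were dosed every 2 weeks, overstating them by a factor between 1 and 2; the text also gives 42-fold where Table 9 gives 51.

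*Protocol*

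**What the plan says.** Protocol Section 4.3 bases Part C dose selection on human PK from the earlier cohorts and on "the NOAEL exposures established based on 13-week GLP repeat-dose studies in mouse and cynomolgus monkeys". Tables 8 (intact AMG 133) and 9 (total AMG 133) list the resulting multiples for cohorts 12 and 13.

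- **Formula.** Footnote d of Table 8 takes the animal AUC_last "after 13 weeks (7 doses) of AMG 133 administration in the mouse or monkey x 4/predicted" human AUC over days 0 to 28 after the second dose. Footnote d of Table 9 uses the same factor: "of AMG 133 administration in the mouse or monkey x 4/predicted".
- **Interval of the animal AUC.** Footnotes b and c of both tables label AUC_last as AUC 0-168 h. The abbreviation list under Table 8 defines it as the "area under the concentration-time curve during a last dosing interval".
- **Animal dosing schedule.** Section 2.2.2.3 gives, for mice, "administration of 25, 75, and 150 mg/kg AMG 133 by SC injection once every 2 weeks for a total of 7 doses" and, for monkeys, "once every 2 weeks SC administration of 20, 60, or 120 mg/kg AMG 133 for 13-weeks (7 total doses". Section 4.3 repeats the schedule: "toxicology studies (every 2 weeks dosing, Section 2.2.2.3".
- **Text against table.** For total AMG 133 in cohort 12, Section 4.3 gives the mouse multiples as "54-fold and 42-fold for" Cmax and AUC respectively, and cites Tables 8 and 9. Table 9 gives 54.3 and 51.

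**The concern.** A 28-day human AUC should be compared with the animals' exposure over 28 days on the schedule they actually received. Multiplying a 168-h AUC by 4 does this only if the animals were dosed weekly, or if exposure in the second week after a dose equals that in the first. The studies dosed every 14 days, and the documents give no evidence that the two weeks are equal.

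The description of the animal AUC is also inconsistent. On a 14-day schedule, the last dosing interval is 336 h, not the 168 h on the label. If the definition is the correct part, the multiplier should be exactly 2.

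These multiples are stated safety cover for Part C. Investigators and ethics reviewers read of about 41- to 51-fold AUC cover, which the toxicology schedule does not support as calculated, and one margin appears with two values. No endpoint or statistical analysis uses these figures. Part C also rests on human data from earlier cohorts. No dose is questioned here.

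**Working it through.** **Inputs (Section 4.3, Tables 8 and 9 and their footnotes)**

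Animal AUC 0-168 h after the last dose, in µg·hr/mL:

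| | Intact | Total |
|---|---|---|
| Mouse | 188 000 | 291 000 |
| Monkey | 200 000 | 279 000 |

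Predicted human AUC, in µg·hr/mL:

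| | Intact | Total |
|---|---|---|
| Cohort 12 | 17 731 | 22 831 |
| Cohort 13 | 18 513.6 | 24 504 |

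Table 9 heads the human column AUC_tau; I take it to be the 0-28 day AUC that its footnote d names.

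**Step 1. Reproduce the stated figures.** Multiple = 4 × animal AUC 0-168 h / human AUC. For intact mouse, cohort 12: 4 × 188 000 / 17 731 = 42.41, stated as 42.4. All eight AUC multiples reproduce this way (table in Step 3), so the factor 4 was applied to the tabulated AUCs and is not just a misprint in the footnote.

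**Step 2. Match the schedule.** 28 days of dosing every 14 days contain two dosing intervals. Let r = AUC 168-336 h / AUC 0-168 h. Then:

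- 28-day animal exposure = 2 × AUC 0-336 h = 2(1 + r) × AUC 0-168 h.
- Overstatement from using 4 = 4 / [2(1 + r)] = 2 / (1 + r).

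The documents do not give r. For r from 0 to 1 the multiplier runs from 2 to 4 and the overstatement from 2 to 1: r = 0.25 gives 1.60, r = 0.5 gives 1.33, r = 0.75 gives 1.14. If AUC_last is really the full 336-h interval, the multiplier is 2 and the overstatement exactly 2.

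**Step 3. Bounds on each margin**

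| Margin | Stated | Recomputed with ×4 | Lower bound (×2) |
|---|---|---|---|
| Intact, cohort 12, mouse | 42.4 | 42.41 | 21.2 |
| Intact, cohort 12, monkey | 45.1 | 45.12 | 22.6 |
| Intact, cohort 13, mouse | 40.6 | 40.62 | 20.3 |
| Intact, cohort 13, monkey | 43.2 | 43.21 | 21.6 |
| Total, cohort 12, mouse | 51 | 50.98 | 25.5 |
| Total, cohort 12, monkey | 48.9 | 48.88 | 24.4 |
| Total, cohort 13, mouse | 47.5 | 47.50 | 23.8 |
| Total, cohort 13, monkey | 45.5 | 45.54 | 22.8 |

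**Step 4. Where within the range? (illustration only)** Assume one-phase decline from Cmax. Mean first-week concentration over Cmax is then (1 − e^−x)/x, where x is the decline over 168 h, and r = e^−x. The footnotes give AUC/(168 × Cmax):

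| | AUC/(168 × Cmax) | r | 2(1 + r) | Overstatement |
|---|---|---|---|---|
| Intact mouse | 188 000/(168 × 1590) = 0.704 | 0.473 | 2.95 | 1.36 |
| Intact monkey | 200 000/(168 × 1500) = 0.794 | 0.618 | 3.24 | 1.24 |
| Total mouse | 291 000/(168 × 2360) = 0.734 | 0.520 | 3.04 | 1.32 |
| Total monkey | 279 000/(168 × 1960) = 0.847 | 0.711 | 3.42 | 1.17 |

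On this assumption the cohort 12 intact margins would be about 31 (42.41/1.36) for mouse and 36 (45.12/1.24) for monkey.

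A second assumption is first-order SC absorption with half-life 6 to 36 h, seven doses every 336 h, and elimination fitted to the same ratios. The overstatement is then 1.47-1.68 (intact mouse), 1.31-1.46 (intact monkey), 1.41-1.62 (total mouse) and 1.22-1.29 (total monkey).

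**Step 5. Text against table.** Total, mouse, cohort 12: 4 × 291 000 / 22 831 = 50.98. This agrees with Table 9 (51) and not with the text (42).

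**Step 6. Cmax multiples.** These do not use the factor 4 and they reproduce, for example 1590/37 = 43.0 and 2360/43.5 = 54.3. They do so only if the animal Cmax is in µg/mL; the footnotes print mg/mL.

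**The case against.** The strongest reply is that the 0-168 h label is probably right and the definition is loose wording. The label appears in four footnotes, and a factor of 4 reaches 28 days only from 168 h. Seven doses every 14 days put the last on day 85, and 13 weeks end on day 91, so perhaps only one week was sampled after the last dose. The day-85 intact-to-total ratios in the nonclinical PK section fit this: up to 0.65 in mouse and 0.72 in monkey, against 188/291 = 0.65 and 200/279 = 0.72 here. On that reading the ×2 values would require no exposure at all in the second week. The same PK section says exposure to intact drug was maintained throughout, and none of the illustrations above reaches 2. Last-dose data from 168 to 336 h may also not exist. Finally, the scaling is disclosed, the documents set no minimum margin, the Cmax margins stand, and the misprinted 42 is lower than the table value, so it does not inflate cover.

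Much of this stands. It makes an overstatement of exactly 2 less likely, it shows that ×2 is a floor and not an estimate, and it means recomputation may not be possible from last-dose data. It does not rescue the factor of 4. One week of sampling would explain the 168-h label, but not treating that week as recurring every 7 days when doses were 14 days apart. Disclosing the formula does not make it match the schedule.

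**Conclusion.** The concern holds. The AUC multiples in Tables 8 and 9, and the Section 4.3 text that repeats them, use a weekly scaling that does not match dosing every 2 weeks. They are overstated by a factor between 1 and 2; a factor of 1 would need equal exposure in the two weeks after a dose. The range assumes that second-week exposure is no higher than first-week exposure. The exact size cannot be determined from the documents, and the illustrative 1.17 to 1.68 rests on assumed kinetics. The smallest stated margin, 40.6, falls no lower than 20.3.

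The conflict between the AUC_last definition and its label, and the conflict between 42 and 51, are both certain. The second is editorial and adds no weight to the scaling point. Because these are stated safety margins in the Part C dose rationale, they should be corrected.

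**What to change.** - State whether AUC_last covers 0-168 h or the full 336-h dosing interval, and make the definition and the footnotes agree.
- Recompute the AUC multiples as 2 × animal AUC 0-336 h / human AUC 0-28 days. If only the 0-168 h AUC exists, report each multiple as a range from ×2 to ×4, with the ×2 value labelled a lower bound and the assumption on second-week exposure stated.
- Restate Tables 8 and 9 and the Section 4.3 text from the same calculation, and reconcile 42-fold with 51.
- As editorial clean-up, reconcile the animal Cmax unit (mg/mL, against µg/mL for humans), and footnote e's reference to a human single dose with the tables' second-dose definition. Neither changes a tabulated multiple.

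The cost is a recalculation from existing toxicokinetic data, or a restated range, plus text edits. No new data collection is needed. The downside is that the stated AUC margins become less favourable.

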4.4 End of Study

4.4.1 End of Study Definition

Primary Completion: The primary completion date is defined as the date when the last subject is assessed or receives an intervention for the final collection of data for the primary endpoint(s).

If the study concludes prior to the primary completion date originally planned in the protocol (ie, early termination of the study), then the primary completion will be the date when the last subject is assessed or receives an intervention for evaluation in the study (ie, last subject last visit).

End of Study: The end of study (EOS) date is defined as the date when the last subject across all sites is assessed or receives an intervention for evaluation in the study (ie, last subject last visit), following any additional parts in the study (eg, long-term follow-up, additional antibody testing), as applicable.

4.4.2 Study Duration for Subjects

The planned duration of participation in the study is approximately 178 days for Part A, 235 days for Part B, **and up to 235 days for Part C.**

4.5 Patient Input on Study Design

Patient input was not obtained in the design of this study.

5. Study Population

Investigators will be expected to maintain a screening log of all potential study candidates that includes limited information about the potential candidate (eg, date of screening). This log may be completed and updated through an Interactive Response Technology (IRT).

Eligibility criteria will be evaluated during screening.

Before any study-specific activities/procedures, the appropriate written informed consent must be obtained (see Section [11.3](#)).

Prospective approval of protocol deviations to recruitment and enrollment criteria, also known as protocol waivers or exemptions will not be provided.

5.1 Inclusion Criteria

Subjects are eligible to be included in the study only if all of the following criteria apply:

- 101 Subject has provided informed consent before initiation of any study-specific activities/procedures.
- 102 Age \geq 18 years to \leq 65 years, at the time of signing the informed consent.
- 103 Except for obesity, otherwise healthy as determined by the investigator or medically qualified designee based on a medical evaluation including medical history, physical examination, laboratory tests, and ECGs on day -2 (cohorts 1 to 6, cohort 11 to 13) or day -1 (cohorts 7 to 10) and screening.
- 104 BMI between \geq 30.0 kg/m² and \leq 40.0 kg/m².
- 105 Have a stable body weight (< 5 kg self-reported change during the previous 8 weeks) before screening.
- 106 Willing to maintain current general diet and physical activity regimen, except for the physical activity in the 72 hours before each blood sample collection for the clinical laboratory analysis, which should not be strenuous.
- 107 Females must be of nonreproductive potential
 - Postmenopausal as defined as:
 - Age of \geq 55 years with no menses for at least 12 months; OR
 - Age < 55 years with no menses for at least 12 months AND with a follicle-stimulating hormone level $>$ 40 IU/L or according to the definition of “postmenopausal range” for the laboratory involved; OR
 - History of hysterectomy; OR
 - History of bilateral oophorectomy.
- 108 For patients in cohorts 7 to 10 only, subjects must have a smartphone device with the capability of downloading apps or other digital tools required for this cohort.

